The study will produce scientifically strong evidence as to whether two alternative models of community HIV screening among FSW (assisted and unassisted) result in (1) increased rates of formal HIV testing at health facilities and (2) increased rates of treatment initiation in districts in which the community screening intervention is added to the existing FSW community outreach model.

Two alternative study protocols are described in this document. The bulk of this document presents a protocol for a community randomized controlled trial (cRCT), which is the preferred research design option. However, due to a delay in procurement of the OraQuick® rapid HIV test kits that are to be used in the study, there may be insufficient time to undertake a full cRCT.¹ Accordingly, a contingency protocol that can be implemented in a shorter period of time is also presented.

6. Study Objectives

The primary objectives of this study will provide answers to the following five (5) questions:

1. Does the proportion of FSW who know their HIV status increased?

¹ All research activities must be completed by 31 December 2020.

2. Does the introduction of community HIV screening among FSW increase the rate of HIV testing at health facilities?
3. Does “assisted” or “unassisted” community HIV screening among FSW result in a larger increase in the rate of HIV testing at health facilities?
4. Does “assisted” and “unassisted” community HIV screening among FSW results in a larger increase in the rate of HIV positive case finding?
5. Does the introduction of community HIV screening among FSW increase the rate of initiation of ART?

The secondary objectives of this study will provide answers to the following two (2) questions:

1. What is the acceptability of community-based self-screening for FSWs participating in this study?
2. What is the satisfaction of FSWs participating in this study towards delivery of community-based self-screening?

B. STUDY DESIGN

1. Design Summary

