The flowchart of the study is presented in Figure 1. Randomization was carried out among the 23 priority districts in this study with a ratio of 2:1 (that is, 2 intervention districts per 1 control district). The details of randomization are explained in section B.4 of this document. **The assigned 15 intervention districts and 8 comparison districts** are described in Table 6. Potential participants in the intervention area will be screened through the inclusion and exclusion criteria established for

this study. The criteria for participants who are eligible for this study are explained in section B.3 of this document and Annex2.

According to the Indonesian Ministry of Health's current recommendation, HIV blood test at an authorized health facility is still the current practice for HIV diagnosis. Both participants in the intervention and comparison area will be offered for HIV blood test at a health facility. Participants in comparison areas and participants in intervention areas who agree to take HIV test at a health facility will then be managed further according to the existing guideline or "standard of care." For participants in intervention areas who refuses to have her blood drawn for HIV test at a health facility will then be offered self-testing using OraQuick®. Participants will then fill and sign the informed consent to participate in CBS study.

Next, participants will be offered to do the test assisted or unassisted. If the participant chooses to perform the test assisted, the PL/PE will help her from filling in a baseline survey, performing the test, and filling in a post-test survey. If the participant chooses to perform the test unassisted, there will be two options for the participant to get the test kit. First, PL/PE will deliver the test kit for the participant, help with filling in the baseline survey on the spot and give information about uploading test results and the post-test survey, along with a hotline number to call for any questions and concerns, including follow-up steps after participants have received the results. The second method, participants will be given a link online which will entitle information of this study, eligibility criteria, informed consent, baseline survey, link to order a test kit, link to upload result and link to fill in the post-test survey. Participant who chooses this second method will also be given hotline number should there be any further inquiries.

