P_1 = the expected population proportion in the comparison group of districts (set = 0.5 – this is the worst-case scenario and will produced a sample size that is adequate irrespective of the actual proportion)

P_2 = the expected population proportion in the intervention group of districts (set = 0.6 – assume minimum effect size to be realized of 10 percentages points)

$$P = (P_1 - P_2) / 2$$

$(P_1 - P_2)$ = the magnitude of comparison-group differences (or change over time) to be detected with the specified level of precision and power (assumed to be +/- 10 percentage points)

deft = design effect to compensate for clustering at the district level (1.5 assumed).

The required sample size is thus $n \geq 635$ per experimental group; ≥ 761 after 20% allowance for lost-to-follow up

³ Source: Lwanga SK and Lemeshow S. Sample Size Determination in Health Studies: A Practical Manual. Geneva: World Health Organization.

Interpretation: we would need to recruit 761 FSW who self-test for HIV testing in the intervention districts and 761 FSW for HIV testing at health facilities in comparison districts to be able to detect a 10 percentage point difference in the rate of HIV testing at health facilities (intervention vs. comparison districts) to have 95% certainty that a difference of that magnitude would not have occurred by chance and 90% certainty of detecting a difference of this magnitude if such a difference existed.

In order to assess whether “assisted” or “unassisted” community HIV screening among FSW results in a larger increase in the rate of HIV testing at health facilities, we would need samples of size $n \geq 761$ each of FSW who received assisted and unassisted screening in intervention districts, a total of $n \geq 1,522$ FSW in intervention districts, plus $n \geq 761$ in comparison districts.

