Sample size requirements for the third question measurement pertains to the number of FSW who test positive for HIV at a health facility and are thus eligible to initiate treatment. This will depend upon (1) the number of FSW presenting at health facilities for testing and (2) the positivity rate among those tested. Sample sizes should thus be calculated accordingly. If we assume a testing positivity rate of 3%, it is apparent that the expected number of FSWs who would be eligible for treatment will be small and we will lack sufficient statistical power to make meaningful comparisons with comparison districts. For this reason, it is recommended that the impact of community screening among FSW be measured using SIHA data for FSW in both intervention and comparison districts. This estimate of impact derived in this way will be confounded if it were to be the case that interventions other than HIV self-testing were to be better implemented in intervention vs. comparison districts. It might be possible to minimize this potential bias by including measures of intervention implementation performance in the intervention and comparison districts in multivariable analyses. Thus, a large enough sample size is required to ensure sufficient power to determine the difference in the intervention and control districts.

C. THE INTERVENTION

1. General Description of The Intervention

FSW who meet the eligibility criteria will be offered for HIV blood test first. Participants who wish to take the test will then managed according to the current guideline for standard of care. Participants who disagree to take HIV blood test will then be offered screening test with Ora-Quick®. There will be with two options for community HIV screening by Peer Leaders: (1) in a convenient community setting assisted by PL/PE (assisted screening) or (2) in a setting of their own choosing without assistance from PL/PE (unassisted screening). FSW will also be able to access a community-based screening test by following online link from messages spread through WhatsApp number without having to come into contact with outreach workers. The saliva-based Ora-Quick® test kit will be used for community screening.

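### Assisted versus unassisted screening is the participant's choice and partly fixed by contact channel, yet primary Objective 3 treats it as a method effect and analysis item F.3 names no adjustment

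*Combined protocol and SAP*

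**What the plan says.** - **Unit of randomisation (B.1, B.4).** "Randomization was carried out among the 23 priority districts in this study", in a 2:1 ratio of intervention to comparison. Screening method is not part of the allocation.
- **How method is decided (B.1).** A woman in an intervention district who declines a facility blood test is offered a kit. Then: "Next, participants will be offered to do the test assisted or unassisted".
- **Channel (C.1 to C.3).** Assisted screening is limited to women whom an outreach worker has met in person. Unassisted screening can also be reached "from messages spread through WhatsApp number without having to come into contact with outreach workers". A peer leader or educator may hand over an unassisted kit as well, so some women could have had either method and some could not. C.3 lets the details of unassisted screening vary by district.
- **Question (A.6, Objective 3, primary).** It asks whether assisted or unassisted "community HIV screening among FSW result in a larger increase in the rate of HIV testing at health facilities".
- **Size (B.5).** To learn which method "results in a larger increase in the rate of HIV testing at health facilities, we would need samples of size" of at least 761 per method, 1,522 in intervention districts.
- **Analysis (F).** Item 3 compares, between methods, the proportion of screened women who take a confirmatory test. Items 2, 9 and 10 compare characteristics, stigma scores and risk behaviours by method. The introduction to F promises tests suited to each analysis.

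**The concern.** Objective 3 is worded as a causal question and sized with the same 761 per group as the comparison of randomised districts, but nothing in the design makes the two method groups comparable. Women who want a peer beside them may differ from those who order a kit online in anticipated stigma, testing history and how they find clients. Each of these could plausibly affect whether a woman later attends a facility. Section E.1 itself plans to test whether a stigma index predicts facility attendance.

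No section calls the contrast observational or lists self-selection as a limitation. If F.3 is followed as written, a difference produced by selection could be reported as the answer to a primary question and guide which method the programme expands.

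**Working it through.** **1. The plan's own figure.** B.5 gives P1 = 0.5, P2 = 0.6, power 90% and design effect 1.5. With mean proportion P = 0.55,

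n = [z_a √(2P(1−P)) + z_b √(P1(1−P1) + P2(1−P2))]² / (P1−P2)².

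- One-sided z_a = 1.645, z_b = 1.282: n = 422.2, rounded up to 423. Then 423 × 1.5 = 634.5, or 635, and 634.5 × 1.2 = 761.4.
- The printed z_a = 1.96: n = 518.2. Then 518.2 × √1.5 = 634.7, or 635, and 634.7 × 1.2 = 761.6.

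Both routes return 635 and 761. Which one was used does not matter here. The number to carry forward is 635 women analysed per method.

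**2. What selection alone can produce.** Suppose method has no effect. Let a trait lower facility attendance by r, and let its share differ by d between methods. The spurious difference is d × r. The documents give no values, so these are assumptions: attendance is 40% with low stigma and 20% with high stigma, so r = 0.20.

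| High-stigma share, unassisted vs assisted | Attendance, unassisted vs assisted | Spurious difference |
|---|---|---|
| 40% vs 30% | 0.32 vs 0.34 | 0.10 × 0.20 = 2 points |
| 60% vs 30% | 0.28 vs 0.34 | 0.30 × 0.20 = 6 points |

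**3. How often that would look significant.** SE = √(deff × [pu(1−pu) + pa(1−pa)] / 635), and the probability is P(|z| > 1.96).

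| Difference | deff 1.5 | deff 1.0 |
|---|---|---|
| 2 points | SE 0.0323; 9.5% | SE 0.0264; 11.8% |
| 6 points | SE 0.0317; 47.3% | SE 0.0259; 63.9% |

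The nominal rate is 5%. A larger sample makes a false finding more likely, because the bias stays while the SE shrinks. The direction is arbitrary: reversing the shares reverses the sign.

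**4. Does any other section supply the adjustment?** Items F.2, F.9 and F.10 would show measured imbalance, but none is tied to F.3. The only mention of multivariable analysis, in B.5, concerns the treatment question between intervention and comparison districts using SIHA data.

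**5. Are the covariates usable?** E.1 collects them and E.4 links forms by Kit ID. In B.1 the baseline survey comes after the choice, and its mode can differ. For assisted women: "If the participant chooses to perform the test assisted, the PL/PE will help her from filling in a baseline survey, performing the test". For women using the online route: "participants will be given a link online which will entitle information of this study, eligibility criteria, informed consent, baseline survey". Answers on stigma and condom use may therefore not be fully comparable between methods.

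**6. Is the outcome listed alike?** In E.3, row 9 of the main table lists later facility testing after reactive tests only. Item 9 of the additional unassisted list covers reactive and non-reactive results.

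**The case against.** The strongest reply is that selection is narrower than it looks and would be visible. Screened women are meant to share the same eligibility, including no HIV test in six months, and to have declined a facility blood test. Items F.2, F.9 and F.10 set the groups side by side. This stands in part: a careful reader of the report would see measured imbalance. But the F.3 estimate would still be unadjusted, and a valid test of two proportions does not separate method from who chose it.

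A second reply is that the illustration's inputs have no source in the documents. That is correct. They show how the mechanism works and do not predict its size.

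Three stronger readings are tempting, and the documents do not support them.

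- **That the E.3 lists create a large recording artefact against assisted screening.** C.2(g) leaves existing tracking of testing unchanged. C.2(a) and (f) provide referral cards, including for women with non-reactive results. C.5 pays for facility attendance after a non-reactive result under both methods. The content of Annex 1, the recording flowchart, is not available here. Other sources may capture these visits, so no artefact size can be claimed.
- **That Objective 4 has the same flaw.** It asks whether assisted and unassisted "community HIV screening among FSW results in a larger increase in the rate of HIV positive case finding". It joins the methods with 'and', and F.6 brings in the control group, so it may not ask for this contrast.
- **That only women met face to face can give a valid main estimate.** That restriction drops the online women whom the unassisted channel was built to reach, and it needs a contact-channel variable that may not be recorded. It suits a sensitivity analysis.

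**Conclusion.** The concern holds. Objective 3 rests on a self-selected, channel-dependent contrast that is sized and worded as a comparison of method effects and analysed without a specified adjustment. The size and direction of any bias are unknown. The 9-12% and 47-64% figures depend on the assumed attendance rates and stigma shares and on 635 analysed per method.

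Adjustment would improve the estimate but would not make it causal, because unmeasured selection remains. A reader might infer that the trial's main conclusion is undermined. It is not: the comparison of randomised districts does not depend on how women divide between methods.

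**What to change.** 1. **A.6, B.5 and F.3:** state that assisted versus unassisted is a non-randomised contrast that shows association, with residual unmeasured selection.
2. **F.3:** pre-specify as the main estimate for Objective 3 a covariate-adjusted difference among all screened participants. Include district as a factor, plus age, education, where clients are found, last HIV test, condom use and stigma score. Report the unadjusted proportions alongside. Show the estimate with and without stigma and condom use, because survey mode differs by method. Add a sensitivity analysis limited to women met face to face, if contact channel can be identified.
3. **E.3:** align the lists so that facility testing after both reactive and non-reactive results is recorded for assisted as well as unassisted women.

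**Cost.** Wording in three sections, one recording line and modest analysis work on items already collected. If R² between method and covariates is 0.05 to 0.20 (assumed), the interval widens by √(1/(1−R²)) = 1.026 to 1.118, about 3-12%. The claim becomes softer. Women keep their choice of method, and no arm is added.

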
3. Implementation Guidelines: Unassisted Community Screening

Because of differences in the structure of sex work and in the enabling environment in different districts, it will be necessary to develop the details of unassisted community screening on a district-by-district basis. Ideally, the same unassisted community screening intervention would be implemented in the same way in all intervention districts, but if this is not possible due to the factors outlined above, allowing some details to vary across districts is preferable to trying to implement a standard protocol that is expected a priori to fail in some locations.

For unassisted community screening, in which OW don't have face-to-face contact with FSWs, possible mechanisms for distributing Ora-Quick test kits entail:

- a. Trained PE/PL identifying various online networks in which FSWs use to solicit their service.
- b. Trained PE/PL building trust from FSWs to participate in the study.
- c. Trained PE/PL send broadcast message containing brief information of the study, eligibility criteria for participation, step-by-step method to order the kit and have it delivered to their address, short link for description of how to use the kit (flier or short video), and mandatory baseline and post-test survey. Test kit delivery will be done by same-day delivery system (Go-Send/Grab Send) from selected places where the test kit will be stored (Implementing Unit Office or selected health care facilities) to client's address. Trained peer leader/peer educator could also distribute the test kit but not participating in the testing by assisting FSW during the test.

- d. Trained PE/PL carrying out follow-up for FSWs being previously approached for the test. The same trained PE/PL is assigned to be the contact person/hotline for each FSW they approached and agreed to take the test.
- e. FSW send/upload results of the test along with a completed post-test survey. Cash (mobile top-up) incentive will be transferred to FSW who send the test results and post-test survey. Every kit distributed will have unique code and FSW will be asked to fill it in both baseline and post-test survey to ensure one FSW is entitled to only one test kit.

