Except for outreach, all above mentioned activities are incentivized. Below are details of incentives given to PL/PE based on current standard program:

1. Cash incentive of 70,000 IDR for every client who referred for HIV testing to health facilities.
2. Cash incentive of 25,000 IDR for every client taking the test after being reached through mobile outreach.
3. Cash incentive of 50,000 IDR for every client with positive confirmatory test starting on ART.

5. Incentives for Participation

Incentives will be given for different participation role in this study:

1. For all eligible FSWs participating in baseline survey will be given 50,000 IDR
2. For FSWs taking VCT and reporting the results will be given 100,000 IDR
3. For FSWs doing CBS AND uploading/sending test result will be given 100,000 IDR
4. For FSWs participating in post-test survey (both assisted and unassisted) will be given 50,000 IDR
5. Cash incentive 100,000 IDR for transportation and registration and/or fee for confirmatory test for CBS **reactive result** for FSWs who go to health care facility for confirmatory test (assisted and unassisted)
6. Cash incentive 100,000 IDR for transportation and registration and/or fee for confirmatory test for CBS **non-reactive result** for FSWs who go to health care facility for confirmatory test (assisted and unassisted)

Incentives will be given for different role of PL/PE in this study:

1. For PL/PE who assists FSWs for taking self-screening (including filling in baseline and post-test) will be given 150,000 IDR
2. For PL/PE who delivers test kit to FSWs who opt for unassisted screening AND obtain baseline survey on the spot will be given 100,000 IDR

Incentives will be given for health facility:

For collecting data on FSWs who do confirmatory test (assisted and unassisted). Funds to cover additional operational cost will be given to each implementing unit (IU) for delivering test kit via Go-Pay/Grab Pay Top-Up to client's address.

D. LINKAGE TO HEALTH SERVICES FOR ARV INITIATION

Outreach workers will navigate clients to health care facilities for confirmatory test and ARV initiation if the result is confirmed as positive. Health care facilities in each district will be selected by their readiness to offer Test & Treat (T&T). Clients who come for confirmatory test are expected to be started for ARV initiation on the same day of confirmatory test.

E. DATA COLLECTION PROTOCOLS

1. Baseline survey

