In the event that participants' data are collected by paper, a procedure to upload the data into the established online system will be developed. Each data manager in the IUs needs to conduct the procedure regularly. This is to ensure that all data are being captured thoroughly.

F. DATA ANALYSES

The data analyses to be undertaken will be directed to addressing the research questions laid out at the beginning of the protocol and statistical tests appropriate to each specific analysis will be performed to inform the interpretation of results. The specific steps in the data analysis will be as follows:

1. Compare the characteristics of FSWs who receive self-testing and blood testing.

2. Compare the characteristics of FSWs who receive assisted and unassisted self-testing.
3. Compare proportion of FSWs taking confirmatory test out of those who receive the test in the assisted and unassisted self-testing.
4. Compare the proportion of FSWs who receive HIV test out of those who got offered for the test (including self-testing) in the intervention group with proportion of FSWs who receive HIV test in the control group.
5. Compare the proportion of FSWs taking confirmatory test (including self-testing) out of those receive the test in intervention groups and control group.
6. Compare the proportion of HIV positive in the assisted, unassisted (intervention) and HIV positive in the control group.
7. Compare the proportion of ART initiation in the assisted, unassisted (intervention) and the control group.
8. Calculate the cascade of HIV testing and treatment.
9. Compare stigma scores and FSWs who went to a health facility for HIV testing between assisted, unassisted group.
10. Compare the HIV and STI risk behaviors between assisted and unassisted group.

G. CONTINGENCY STUDY DESIGN

Should the OraQuick® test kits not become available in sufficient time to conduct a full-scale cRCT, a smaller-scale study will instead be undertaken. The purpose of the smaller study is the same as the cRCT described above, and the same protocol described above will be implemented. But the comparison is achieved targets between before and after intervention – there will be no comparison districts. The study will be undertaken in three (3) districts. The three districts will be selected from different parts of Indonesia, and they are: Kota Bandung (west part of Indonesia), Kota Denpasar (central part of Indonesia), and Kota Makassar (center-east part of Indonesia).

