Annex 8. Post-test Survey Questionnaire

KIT Code		0	1	-	0	0	1
Participant Code (First 4 letters, year, month, day)							
Name of OW/PE							
1.	Please write your full name or initials						
2.	How was the clarity of the information about HIV test kit you received/obtained? (Select one answer)	1. Extremely unclear					
		2. Unclear					
		3. Fairly clear					
		4. Clear					
		5. Extremely clear					
3.	When you performed HIV self-testing, was there any person (peer) who assisted you?	1. Yes					
		2. No					
4.	How easy was performing an HIV test using the self-testing kit given? (Select one answer)	1. Extremely difficult					
		2. Difficult					
		3. Fairly difficult					
		4. Easy					
		5. Extremely easy					
5.	What was the reason that prevented you from testing using the test kit provided?	1. Extremely difficult					
		2. Difficult					
		3. Fairly difficult					
		4. Easy					
		5. Extremely easy					
6.	This question only applies for those who underwent the self-testing assisted by OW/PE. How would you rate the given support by OW/PE /contact people who accompanied/contacted you during HIV self-testing? (Select an answer)	1. Extremely unclear					
		2. Unclear					
		3. Fairly clear					
		4. Clear					
		5. Extremely clear					
7.	This question only applies if your test results are negative. How much do you want to take an HIV test regularly after taking this test?	1. Extremely not in favour					
		2. Less in favour					
		3. Fairly in favour					
		4. In favour					
		5. Very in favour					
8.	How was your experience in performing this HIV self-testing (saliva test)?	1. Extremely unpleasant					
		2. Unpleasant					
		3. Fairly pleasant					

		4. Pleasant
		5. Extremely pleasant
9.	How sure are you with the accuracy of this test	1. Very doubt
		2. Less sure
		3. Fairly sure
		4. Sure
		5. Very sure
10.	How was your test result?	1. Positive
		2. Negative
		3. Indeterminate
11.	How much do you want to confirm your test results to the healthcare facilities?	1. Extremely unlikely
		2. Fairly unlikely
		3. Fairly likely
		4. Likely
		5. Extremely likely
12.	How likely are you to recommend your peers to undergo the screening test that you just performed?	1. Extremely unpleasant
		2. Unpleasant
		3. Fairly pleasant
		4. Pleasant
		5. Extremely pleasant
13	How much do you trust the accuracy of the test result	1. Extremely unsure
		2. Fairly unsure
		3. Fairly sure
		4. Sure
		5. Extremely sure
14.	What was your test result?	1. Positive → P.13

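### Assisted women fill in the post-test survey with help from the paid peer it names and asks them to rate, while unassisted women return it themselves, so acceptability and satisfaction results are open to courtesy bias

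*Combined protocol and SAP*

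**What the plan says.** **Assisted route.** B.1 states that "the PL/PE will help her from filling in a baseline survey, performing the test, and filling in a post-test survey". C.5 prices this as one package: "For PL/PE who assists FSWs for taking self-screening (including filling in baseline and post-test) will be given 150,000 IDR".

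**Post-test form.** Annex 8 has a field for the outreach worker's or peer's name. Question 6 asks "How would you rate the given support by OW/PE /contact people who accompanied/contacted you during HIV self-testing", and its lead-in says "This question only applies for those who underwent the self-testing assisted by OW/PE". Women in either route can answer the items on clarity, ease, pleasantness, confidence in accuracy, intention to confirm and willingness to recommend.

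**Unassisted routes.** In the online route B.1 supplies a "link to upload result and link to fill in the post-test survey", along with links for consent, baseline survey and kit order. In the delivered-kit route the peer will "help with filling in the baseline survey on the spot" but only informs the woman about the post-test survey. C.3(e) then has the woman return it: "FSW send/upload results of the test along with a completed post-test survey". C.5 pays the delivering peer 100,000 IDR for delivery plus the baseline survey, with no mention of the post-test.

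**Use of the data.** Secondary objectives 1 and 2 are acceptability and satisfaction with delivery. Section F compares assisted with unassisted women on characteristics (step 2), stigma scores and facility attendance (step 9), and, in step 10, "Compare the HIV and STI risk behaviors between assisted and unassisted group".

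**The concern.** A woman who answers with the help of the person she is rating, and who may want to please that person, has reason to answer kindly. The same applies to rating the experience that person has just led her through. Here the helper is also paid for a package that includes the form. If assisted ratings are inflated in this way, the satisfaction result for that route is too favourable. An apparent preference for assisted over unassisted screening could then reflect only how the form was completed. Enlarging the sample narrows the confidence interval around such a shift but does not remove it. If completion mode is not recorded at the time, it may not be recoverable at analysis.

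**Working it through.** **1. Who helps with which survey (B.1, C.3, C.5)**

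| Route | Baseline survey | Post-test survey | Peer fee covers |
|---|---|---|---|
| Assisted | peer helps | peer helps | test, baseline, post-test (150,000 IDR) |
| Unassisted, kit delivered by peer | peer helps | woman sends it herself | delivery, baseline (100,000 IDR) |
| Unassisted, online | by link | by link | no survey fee listed |

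For the post-test survey, screening method and completion mode coincide: assisted means peer-helped, and both unassisted routes mean self-returned. For the baseline survey, two of the three routes share peer help and only the online route differs.

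**2. Is mode recorded or controlled anywhere?** Annex 8 question 3 asks whether someone assisted with the test, not with the form. The name fields on the survey forms identify the peer, not who entered the answers. E.1 allows entry on the peer's or the woman's phone, and E.4(d) allows paper. I found no independent interviewer, no private completion for assisted women, no field for who completed the form, and no adjustment for mode in section F.

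**3. Which results are exposed?**
- Question 6 is for assisted women only. It can distort the assisted satisfaction estimate but not an assisted-unassisted contrast.
- The shared post-test items feed the two secondary objectives. Section F lists no step that compares them by method, so the contrast problem arises if they are reported side by side.
- Steps 2, 9 and 10 rest on baseline items, so mode matters there only through the online women.
- Facility testing and ART initiation come from routine recording (E.3), not from these ratings.

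**4. The plan's sample size, for scale (B.5).** With P1 = 0.5, P2 = 0.6 and mean 0.55, a one-sided z of 1.645 and 1.282 for power:

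n = [1.645 × sqrt(2 × 0.55 × 0.45) + 1.282 × sqrt(0.25 + 0.24)]² / 0.10² = 422.2, rounded up to 423.

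423 × 1.5 = 634.5 (stated 635), and 634.5 × 1.2 = 761.4 (stated 761). The printed z of 1.96 gives 519 × 1.5 = 779 instead; that is a separate matter and nothing here depends on it. B.5 applies 761 to each screening method.

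**5. Illustration for a shared post-test item.** The documents give neither an SD nor a mode effect. I assume a pure mode shift of 0.2 points and an SD of 0.8 to 1.2, with the plan's design effect of 1.5.

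SE = SD × sqrt(2 × 1.5 / n); probability of significance ≈ Φ(0.2/SE − 1.96).

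| n per method | SD | SE | 0.2/SE | Probability |
|---|---|---|---|---|
| 761 | 0.8 | 0.050 | 3.98 | 0.98 |
| 761 | 1.2 | 0.075 | 2.65 | 0.76 |
| 635 | 0.8 | 0.055 | 3.64 | 0.95 |
| 635 | 1.2 | 0.082 | 2.42 | 0.68 |

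The 635 rows take n before the 20% loss allowance.

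**6. Illustration for a baseline proportion.** With n = 761 the SE is at most sqrt(2 × 0.25 × 1.5 / 761) = 0.0314. Suppose self-completion shifts an answer by 10 points and a share f of unassisted women come online (both assumed). The contrast then moves by f × 10 points:
- f = 1: 0.10/0.0314 = 3.2 SE
- f = 0.5: 0.05/0.0314 = 1.6 SE
- f = 0.25: 0.025/0.0314 = 0.8 SE

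The documents do not give f.

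**The case against.** The best defence is that the plan says the peer helps, not that the peer interviews or records. The fee does not vary with the rating given. The secondary objectives are descriptive, and no listed step contrasts satisfaction by method. Women choose their own method, so assisted-unassisted differences are non-causal in any case. Some women will need reading help.

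Much of this stands. The documents show an exposure to bias, not its size. Upward bias is an expectation about courtesy, not a documented fact. Self-selection is a separate problem and limits any causal reading of steps 2, 9 and 10.

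A reader might go further and infer that steps 9 and 10 are generally distorted because unassisted women answer alone. The documents do not support that: delivered-kit women also get paid peer help with the baseline survey, so an effect there is diluted by the unknown online share. Step 9 may also be meant as an association between stigma and facility attendance, as E.1 describes, and not as a contrast of mean stigma by method.

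The defence does not answer the post-test point. Even a descriptive satisfaction figure is weakened when the rated person helps with the form, and the shared ratings cannot be read across methods when mode and method coincide.

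**Conclusion.** The point holds for the post-test survey. Satisfaction and acceptability among assisted women are open to courtesy bias, and any comparison of the shared ratings by method is confounded with completion mode. For baseline stigma and risk items it holds only for the part of the unassisted group that enrols online. The primary testing and ART outcomes are not affected.

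The size is unknown. The probabilities of 0.76 to 0.98 (0.68 to 0.95 at 635 per method) rest on an assumed 0.2-point shift and assumed SDs. They show only that a modest shift could pass for a real difference. It would be tempting to take the 3.2 SE figure as the expected effect on step 10, but that requires an assumed 10-point shift and every unassisted woman to be online. This is an inexpensive improvement to secondary results, worth making before data collection.

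**What to change.** - **B.1 and Annex 8:** assisted women complete the post-test survey privately on a phone, using the same form or link as unassisted women. The peer steps away unless reading help is needed.
- **C.5:** do not make the peer's fee for an assisted test depend on filling in the post-test form.
- **Baseline and post-test forms, all women, all routes:** add one field for who completed the form (the woman alone, with peer help, or entered by the peer).
- **Section F:** report post-test ratings by that field. Run steps 2, 9 and 10 adjusted for completion mode or stratified by it.
- **If private completion is extended to sensitive baseline items, including STI:** apply it to assisted and delivered-kit women alike. Moving only assisted women would create a mode difference between two routes that now share one.

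The cost is wording in the protocol, forms, SOP and incentive schedule, plus one data field. E.1 already plans phone entry. Some women with low literacy will still need help, which the field will show, and a few post-test forms may be less complete. No change to the sample size is needed.
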